2.2.2 Preclinical and Clinical Studies

Refer to the IB for information on preclinical and clinical studies conducted with VARIVAXTM.

2.2.3 Ongoing Clinical Studies

Refer to the IB for information on ongoing studies with VARIVAXTM.

2.2.4 Information on Other Study-related Therapy

Refer to the IB for VARIVAXTM.

2.3 Benefit/Risk Assessment

It cannot be guaranteed that participants in clinical studies will directly benefit from treatment during participation, as clinical studies are designed to provide information about the safety and effectiveness of an investigational medicine.

In the VARIVAX[™] clinical development program, a single dose of VARIVAX[™] has been shown to be highly efficacious in the prevention of varicella in children ≤12 years of age by multiple, complementary methods, including a placebo-controlled study, evaluation of the varicella attack rate following household exposure, and long-term follow-up of vaccinated cohorts in comparison to historical controls. Postvaccination breakthrough cases of varicella were significantly milder than wild-type disease. Studies with 2 doses of VARIVAX[™] demonstrated a significant increase in vaccine efficacy as compared with a 1-dose regimen, regardless of whether the 2 doses were administered 3 months or 3 to 6 years apart. Although it is more difficult to estimate vaccine efficacy in adolescents/adults, administration of 2 doses of VARIVAX[™] 4 to 8 weeks apart is associated with very low rates of postvaccination breakthrough disease and protection against household exposure to varicella. The data from the clinical development program are supported by postmarketing studies of vaccine effectiveness.

With approximately 226 million marketed doses of VARIVAXTM distributed worldwide from market introduction to 16-MAR-2018, the postmarketing safety profile continues to support the positive benefit/risk ratio of the vaccine.

Additional details regarding specific benefits and risks for participants participating in this clinical study may be found in the accompanying IB and informed consent documents.

3 HYPOTHESES, OBJECTIVES, AND ENDPOINTS

The following objectives and endpoints will be evaluated in Russian individuals 12 months to 75 years of age with a negative clinical history of varicella and/or herpes zoster. No formal hypotheses will be tested in the study.

V210-058-05 FINAL PROTOCOL

Objectives	Endpoints			
Primary				
Objective: To describe the immunogenicity of VARIVAXTM after: • Two doses of VARIVAXTM, given 6 weeks apart, in adults 18 to 75 years of age (Stage 1). • Two doses of VARIVAXTM, given 6 weeks apart, in adolescents 13 to 17 years of age (Stage 2). • One dose of VARIVAXTM in children 12 months to 12 years of age (Stage 2).	 Participants who are seronegative at baseline (baseline VZV antibody titer <1.25 gpELISA units/mL): Antibody response rate (percentage of participants with VZV antibody titer ≥5 gpELISA units/mL at 6 weeks postvaccination for children and at 6 weeks postdose 2 for adolescents/adults). Geometric mean titers (GMTs) of VZV antibody as measured by gpELISA at 6 weeks postvaccination for children and at 6 weeks postdose 2 for adolescents/adults. VZV seroconversion rate (percentage of participants with VZV antibody titer ≥1.25 gpELISA units/mL at 6 weeks postvaccination for children and at 6 weeks postdose 2 for adolescents/adults). Participants who are seropositive at baseline (baseline VZV antibody titer ≥1.25 gpELISA units/mL): GMTs at Day 1 and 6 weeks postvaccination for children and at Day 1 and 6 weeks postdose 2 for adolescents/adults. Geometric mean fold rise (GMFR) from Day 1 to 6 weeks postvaccination for children and f			

C Confidential

Secondary	
Objective: To summarize the safety and tolerability of VARIVAXTM.	 Following each vaccination with VARIVAXTM: Solicited injection-site reactions (redness, swelling, and pain/tenderness) of any intensity or size from Day 1 through Day 5 postvaccination. Unsolicited injection-site adverse events from Day 1 through Day 42 postvaccination. Maximum reported temperature ≥39.0°C oral equivalent from Day 1 through Day 28 postvaccination. Varicella-, and herpes zoster-like rashes occurring from Day 1 through Day 42 postvaccination. Systemic adverse events from Day 1 through Day 42 postvaccination. Serious adverse events from Day 1 through Day 42 postvaccination. Vaccine-related serious adverse events and death from Day 1 through the end of the study period (42 days following the last vaccination) for each participant.
	A summary of blood and urine tests performed 3 days following each vaccination for participants 7 years of age and older.

4 STUDY DESIGN

4.1 Overall Design

V210-058-05 FINAL PROTOCOL

This is an open-label, multicenter, single-arm bridging study to evaluate the immunogenicity of VARIVAXTM in healthy Russian individuals. This study will be conducted as a staged approach as outlined in Table 1, with approximately 150 participants. Participants 12 months of age to 75 years of age (inclusive) with a negative clinical history of varicella (ie, history of a generalized, pruritic, papulovesicular rash, often associated with fever) and/or herpes zoster (painful, dermatomal, papulovesicular rash), are eligible for enrollment in the study.

18-APR-2019

18-APR-2019

PRODUCT: V210
PROTOCOL/AMENDMENT NO.: 058-05

Note: The Stage 1 portion of the study will be conducted and completed first. The Stage 2 portion of the study will commence once an acceptable document for the Stage 1 portion of the study, such as a Clinical Study Report (CSR), has been submitted to the Russian Ministry of Health.

Enrollment will end when the minimum enrollment is attained for each age group as indicated in Table 1. For Stage 2, a minimum of 30 participants will be enrolled per age group, for a total of 100 participants overall.

	T		Б :				
	Target		Duration				
Intervention	(Approximate)	VARIVAXTM	(from first visit				
Groups	Enrollment (n)	Vaccination(s)	to last contact)				
Stage 1 (n=50)							
Adults 18 to 75 years of age	50	2 doses given ~6 weeks apart	4 months				
Stage 2 (n=100)							
Adolescents 13 to 17 years of age	Minimum 30	2 doses given ~6 weeks apart	4 months				
Children 7 to 12 years of age	Minimum 30	1 dose	2 months				
Children 12 months to 6 years of age	Minimum 30	1 dose	2 months				

Table 1 Study Design for Adults and Adolescents/Children

Serum samples will be obtained for evaluation of VZV antibody responses by gpELISA at baseline (Visit 1, prevaccination) and at 6 weeks following the last study vaccination (postvaccination for children 12 months to 12 years of age, and postdose 2 for adolescents/adults 13 to 75 years of age).

All participants will be followed for safety for 6 weeks (42 days) following each vaccination. For participants 7 years of age and older, blood samples for complete blood count (CBC) and blood chemistry and a urine sample for urinalysis will be collected prior to vaccination (Visit 1) and 3 days after each vaccination.

In addition, injection-site reactions and general AEs will be evaluated for all participants by an investigator or qualified designee 7 days (-2 days) after each vaccination.

A participant is considered to have completed the study when (1) has received the scheduled number of study vaccinations (1 dose for children or 2 doses for adolescents/adults), (2) all blood samples for the immunogenicity assessment have been collected, and (3) the 42-day safety data post each vaccination have been collected.

Specific procedures to be performed during the study, as well as their prescribed times and associated visit windows, are outlined in the SoA in Section 1.3. Details of each procedure are provided in Section 8.

Confidential

V210-058-05 FINAL PROTOCOL

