	- Solicited injection-site reactions (redness, swelling, and pain/tenderness) of any intensity or size from Day 1 through Day 5 postvaccination.
	- Unsolicited injection-site adverse events from Day 1 through Day 42 postvaccination.
	- Maximum reported temperature ≥39.0°C oral equivalent from Day 1 through Day 28 postvaccination.
	- Varicella-, and herpes zoster-like rashes occurring from Day 1 through Day 42 postvaccination.
	- Systemic adverse events from Day 1 through Day 42 postvaccination.
	- Serious adverse events from Day 1 through Day 42 postvaccination.
	Vaccine-related serious adverse events and death from Day 1 through the end of the study period (42 days following the last vaccination) for each participant.
	A summary of blood and urine tests performed 3 days following each vaccination for participants 7 years of age and older.

PROTOCOL/AMENDMENT NO.: 058-05

Overall Design:

Study Phase	Phase 3
Primary Purpose	Prevention
Indication	Active immunization for the prevention of varicella in individuals 12 months of age and older
Population	Healthy individuals age 12 months to 75 years of age
Study Type	Interventional
Intervention Model	Single Arm
	This is a multi-site study.
Type of Control	No control
Study Blinding	Unblinded Open-label
Masking	No Masking
Estimated Duration of Study	The Sponsor estimates that the study will require approximately 24 months from the time the first participant signs the informed consent/assent until the last participant's last study-related telephone call or visit.

Number of Participants:

V210-058-05 FINAL PROTOCOL

Approximately 150 participants will be allocated as described in Section 4.1.

PRODUCT: V210

PROTOCOL/AMENDMENT NO.: 058-05

Intervention Groups and Duration:

Intervention Groups											
Groups	Intervention Dose Dose Route of Vaccination Group Name Vaccine Strength Frequency Admin. Regimen										
	Stage 1: Adults (18 to 75 years of age)	VARIVAX™	Refer to product labeling	2 doses	SC	2 doses given 6 weeks apart (Day 1 and Day 43 [+14])	Experimental				
	Stage 2: Adolescents (13 to 17 years of age)	2 doses given 6 weeks apart (Day 1 and Day 43 [+14])	Experimental								
	Stage 2: Children (7 to 12 years of age)	VARIVAX™	Refer to product labeling	Single dose	SC	1 dose given on Day 1	Experimental				
	Stage 2: Children (12 months to 6 years of age)	VARIVAX™	Refer to product labeling	Single dose	SC	1 dose given on Day 1	Experimental				

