4.2 Scientific Rationale for Study Design

VARIVAXTM is not currently licensed in Russia. This study will describe the safety, tolerability and immunogenicity of VARIVAXTM in healthy Russian individuals, 12 months through 75 years of age, which represents the age range for which a license is sought. The purpose of this study is to generate sufficient clinical data for VARIVAXTM in the Russian population in order to demonstrate generalizability of the large amount of existing VARIVAXTM clinical data to the Russian population.

The study will be conducted as a staged approach study (2 stages):

Stage 1 participants are adults (n=50) with the age range of 18 years to 75 years (inclusive).

To ensure the age of the participants is well distributed across all age groups, the target enrollment of Stage 2 participants (n=100 total) will be as follows:

- Adolescent 13 to 17 years of age (minimum 30)
- Children 7 to 12 years of age (minimum 30)
- Children 12 months to 6 years of age (minimum 30)

As described below, the dose regimen, immunogenicity endpoints, and safety endpoints utilized in this study are consistent with those of past VARIVAXTM clinical studies. This will allow comparisons to existing global data, in order to bridge the safety, tolerability and immunogenicity of VARIVAXTM observed in global clinical studies to the Russian population.

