4.4.1 Clinical Criteria for Early Study Termination

The clinical study may be terminated early if the extent (incidence and/or severity) of emerging effects/clinical endpoints is such that the benefit/risk ratio to the study population as a whole is unacceptable. In addition, further recruitment in the study or at particular study sites may be stopped due to insufficient compliance with the protocol, Good Clinical Practice (GCP) and/or other applicable regulatory requirements, procedure-related problems or the number of discontinuations for administrative reasons is too high.

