6.3.2 Stratification

No stratification based on age, sex, or other characteristics will be used in this study.

[figure not shown]
Minimum target enrollment by age group is presented in Table 1.

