6.9 Standard Policies

Study site personnel will have access to a central electronic treatment allocation/randomization system (interactive voice response system [IVRS]/interactive web response system [IWRS]) to allocate participants, to assign vaccine to participants and to manage the distribution of clinical supplies. Each person accessing the IVRS system must be assigned an individual unique PIN. They must use only their assigned PIN to access the system, and they must not share their assigned PIN with anyone.

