9.9.2 Sample Size and Power for Safety Analyses

The probability of observing at least 1 SAE in this study depends on the number of participants vaccinated and the underlying incidence of participants with an SAE in the study population. In Stage 1, it is expected that approximately 50 participants will contribute to the analysis of safety Postdose 1. In Stage 2, it is expected approximately 100 participants will contribute to the analysis of safety Postdose 1.

If no serious vaccine-related AEs are observed in this study in Stage 1 with 50 participants evaluable for safety, there will be a 97.5% probability that the true incidence rate is no more than 7.1%. If no serious vaccine-related AEs are observed in this study in Stage 2 with 100 children/adolescents in this study evaluable for safety, there will be a 97.5% probability that the true incidence rate is no more than 3.6%. The estimate of and the upper bound of the 95% CI for the underlying percentage of participants with a serious vaccine-related AEs given various hypothetical observed number of participants with a serious vaccine-related AEs among approximately 50 adult and approximately 100 adolescents/children are provided in Table 9.

V210-058-05 FINAL PROTOCOL 18-APR-2019

Table 9 Estimate of Incidence of Vaccine-Related Serious Adverse Events and Upper Bound of 95% Confidence Interval Based on Hypothetical Number of Participants with Vaccine-Related Serious Adverse Events

Population	Sample Size	Hypothetical Number of Participants With VR-SAE	Estimate of Incidence	Upper Bound of 95% Confidence Interval †
Adult	50	0	0.0%	7.1%
		1	2.0%	10.7%
		2	4.0%	13.7%
Adolescent/children	100	0	0.0%	3.6%
		1	1.0%	5.4%
		2	2.0%	7.0%

[†] Based on the two-tailed exact CI of a binomial proportion given in Collett [Collett, D. 1999].

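### Does the enrolment stop sentence in Section 4.1 let Stage 2 close at a size other than the stated 100?

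*Combined protocol and SAP*

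**What the plan says.** Section 4.1 contains the only rule that ends enrolment on grounds of size: "Enrollment will end when the minimum enrollment is attained for each age group as indicated in Table 1". The sentence after it reads "For Stage 2, a minimum of 30 participants will be enrolled per age group, for a total of 100 participants overall". Table 1 heads the stage with n=100, gives each of the three Stage 2 groups a minimum of 30 and no maximum, and labels its enrolment column as approximate targets. The Stage 1 adult target in the same table is 50.

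The total recurs elsewhere. Section 4.2 says "the target enrollment of Stage 2 participants (n=100 total) will be as follows" and then lists the same three minimums. Section 9.9.2 says "In Stage 2, it is expected approximately 100 participants will contribute to the analysis of safety Postdose 1", and the Stage 2 rows of Table 9 use 100. The synopsis says "Approximately 150 participants will be allocated as described in Section 4.1", which is 50 + 100.

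Section 6.3.2 rules out stratification and adds only that "Minimum target enrollment by age group is presented in Table 1". Section 4.4.1 gives other grounds for halting, for example that "further recruitment in the study or at particular study sites may be stopped due to insufficient compliance with the protocol", but none of them concerns size. Under Section 6.9, sites use a central system "to allocate participants, to assign vaccine to participants and to manage the distribution of clinical supplies".

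**The concern.** A stop rule says when the sites and the allocation system close the study to new participants. This one is written on the age-group minimums alone. Three minimums of 30 make 90, not 100, and no section states that reaching 100 is a condition for closing. The target and the stop condition can therefore be met at different times.

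Two departures seem possible. Stage 2 could close 10 short, which would loosen the safety bounds in Table 9 and leave little room for exclusions from the per-protocol immunogenicity sets in Tables 7 and 8. Alternatively, with no group maximum, the faster groups could keep enrolling until the slowest reaches 30, so that more healthy children and adolescents enter than the plan states. A multicentre study also needs one rule that every site applies in the same way.

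**Working it through.** **Step 1. The sizes (Section 4.1, Table 1, synopsis).**

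- Sum of Stage 2 minimums: 3 x 30 = 90, against a stated 100. The gap is 10/100 = 10%.
- Whole study: 50 + 90 = 140, against about 150 (50 + 100). The gap is 10/150 = 6.7%.

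**Step 2. Safety precision (Section 9.9.2, Table 9).** Table 9 uses the two-sided exact binomial interval. With x events in n participants, the upper limit is the 97.5% quantile of a Beta(x + 1, n - x) distribution. With x = 0 this reduces to 1 - 0.025^(1/n).

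- n = 100, x = 0: 1 - 0.025^(1/100) = 3.62%. Table 9 gives 3.6%, so the plan's figure is reproduced.
- n = 90, x = 0: 1 - 0.025^(1/90) = 4.02%.

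| Events | Table 9 (n = 100) | Recomputed, n = 100 | n = 90 | n = 120 |
|---|---|---|---|---|
| 0 | 3.6% | 3.62% | 4.02% | 3.03% |
| 1 | 5.4% | 5.446% | 6.04% | 4.56% |
| 2 | 7.0% | 7.04% | 7.80% | 5.89% |

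Closing at 90 widens these bounds by 0.4 to 0.8 percentage points, assuming everyone enrolled is evaluable for safety. Closing at 120 narrows them by 0.6 to 1.2 points.

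**Step 3. Immunogenicity precision (Section 9.9.1, Tables 7 and 8).** The larger tabulated per-protocol sizes are 30 adolescents and 60 children, 90 in all. The smaller are 25 and 55, 80 in all. A Stage 2 of exactly 90 would leave no room for exclusions at the larger sizes, but the smaller ones would remain reachable. The plan already shows what that costs. At a response rate of 0.80, Table 7 gives adolescents 0.61 to 0.92 with 30 and 0.59 to 0.93 with 25. It gives children 0.68 to 0.89 with 60 and 0.67 to 0.90 with 55.

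**Step 4. What the stop sentence would do if applied alone.** It can be read in two ways.

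- *Each group closes when it reaches its own minimum.* Stage 2 ends at exactly 90 and cannot overshoot.
- *Every group stays open until all three have 30.* Stage 2 ends at 90 or more. To gauge this, assume that participants arrive independently with constant shares by age group; the documents give neither shares nor arrival pattern. Then P(N <= n) is the multinomial probability that all three counts are at least 30 after n arrivals.

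| Assumed shares (%) | Median N | P(N > 100) |
|---|---|---|
| equal thirds | 102 | 0.594 |
| 30 / 35 / 35 | 105 | 0.665 |
| 25 / 37.5 / 37.5 | 119 | 0.893 |
| 20 / 40 / 40 | 149 | 0.991 |

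With equal shares the 5th and 95th percentiles are 92 and 121, P(N < 100) = 0.357, and P(N = 90) = 0.009. The results move from 102 to 149 purely with the assumed shares. They also suppose that nobody closes the stage at the stated 100.

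**Step 5. The sentence in its place.** The next sentence in the same paragraph joins the per-group minimum to the total of 100. The stop sentence itself points to Table 1, whose Stage 2 heading carries that total. Read together, they say at least 30 in each group and about 100 overall, with 100 - 90 = 10 places not tied to any group. On that reading Table 9 stands as printed.

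**The case for a change.** The strongest case for a change is that a closing rule should not depend on inference. The next sentence states a target, whereas the stop sentence states the condition for ending, and the central allocation system has to be set to one of them. Nor does the text say what happens if the total reaches 100 while one group is still below 30. The word approximate may cover a few participants either way, but not a median of 119 or 149, and clarifying the sentence would cost almost nothing.

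Part of this stands. The stop sentence is incomplete, and no passage expressly makes 100 a closing condition. The over-enrolment argument is weaker. It needs every group to stay open until the slowest fills, yet closing each group at its own minimum is an equally literal reading. It also needs sites and a central system to pass a total that is stated repeatedly, including in the adjoining sentence. The large medians come from assumed recruitment shares; with equal shares the median is 102, in line with a target of about 100. Slow recruitment in one group would be visible to the sponsor in an open-label study with central allocation, and could be managed without new text.

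The low cost of an edit does not establish a need for one. The sentence also governs the Stage 1 adults, so a rewording confined to Stage 2 would remove the only size-based stop for Stage 1.

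**Conclusion.** The wording is inconsistent, but this is a clerical slip that the surrounding text resolves. Those running the study can be expected to enrol at least 30 per Stage 2 group and about 100 in total, as the paragraph and its table together say. The study is descriptive: Section 3 sets no formal hypothesis, Section 9.9.1 says no formal power calculation for immunogenicity fixed the size, and no decision rule uses the bounds in Table 9. If Stage 2 nevertheless closed at the sum of its minimums, the loss would be 10 participants and 0.4 percentage points on the zero-event bound, with immunogenicity precision still available at the smaller sizes in Tables 7 and 8. This conclusion rests on reading the stop sentence with its neighbour and with Table 1, and on the sizes being approximate, as the plan labels them. The likelihood and extent of enrolment beyond 100 cannot be established from the documents and carry no weight here. No change to the plan follows.

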4.2 Scientific Rationale for Study Design

VARIVAXTM is not currently licensed in Russia. This study will describe the safety, tolerability and immunogenicity of VARIVAXTM in healthy Russian individuals, 12 months through 75 years of age, which represents the age range for which a license is sought. The purpose of this study is to generate sufficient clinical data for VARIVAXTM in the Russian population in order to demonstrate generalizability of the large amount of existing VARIVAXTM clinical data to the Russian population.

The study will be conducted as a staged approach study (2 stages):

Stage 1 participants are adults (n=50) with the age range of 18 years to 75 years (inclusive).

To ensure the age of the participants is well distributed across all age groups, the target enrollment of Stage 2 participants (n=100 total) will be as follows:

- Adolescent 13 to 17 years of age (minimum 30)
- Children 7 to 12 years of age (minimum 30)
- Children 12 months to 6 years of age (minimum 30)

As described below, the dose regimen, immunogenicity endpoints, and safety endpoints utilized in this study are consistent with those of past VARIVAXTM clinical studies. This will allow comparisons to existing global data, in order to bridge the safety, tolerability and immunogenicity of VARIVAXTM observed in global clinical studies to the Russian population.

